## 1.6. Study Rationale

Due to the restrictive nature of the diet and limitations of current treatment, there remains an unmet medical need for new treatments for people with PKU. Given the favorable safety profile of SYNB1934 and the closely related strain SYNB1618 to date, gut-restricted mechanism of action, and demonstrated potential for clinical benefit as shown by blood Phe lowering in PKU participants in study SYNB1618-CP-003, further clinical development of SYNB1934v1 as a potential treatment for PKU is warranted.

PKU participants on sapropterin who do not reach the treatment target of blood Phe  $\leq 360 \mu\text{mol/L}$  could benefit from addition of SYNBI934v1 in the management of blood Phe. Given the differing mechanisms of action of SYNBI934v1 and sapropterin, and different sites of action (sapropterin acting intracellularly in the liver on PAH activity, and SYNBI934v1 acting locally in the GI tract on Phe degradation), interaction between these 2 agents should not be anticipated. Participants on sapropterin enrolled in prior studies have had similar safety and PD compared to the overall population. Participants on a stable dose of sapropterin and stable diet, with blood Phe  $> 360 \mu\text{mol/L}$  are eligible for this study; therefore, any additional blood Phe lowering in SYNBI934v1-treated participants could be attributed to the IMP.

Based on the mechanism of action of the strain and data in prior clinical studies, there is a linear relationship between the dose and Phe metabolism, which has not reached a plateau at the maximum dose studied ( $2 \times 10^{12}$  live cells). Dosing is limited by GI tolerability which appears to be variable across individuals. Titration of dose over time has led to improved tolerability. Blood Phe lowering has been demonstrated at a dose of  $3 \times 10^{11}$  live cells with the closely related strain SYNBI1618, and this dose will be the lowest potential iTD for the study. Data from study SYNBI1618-CP-003 show that a higher dose leads to increased Phe lowering potential and thus, improved clinical benefit. Therefore, in dose-escalating, open-label period (DEP) participants will titrate to their individual titrated dose (iTID) over time guided by AEs in order to achieve the maximum clinical benefit

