### 3.2. Dosing and Dose Escalation

SYNBI934v1 will be taken with a meal throughout the study. Participants will take a proton pump inhibitor (PPI) once per day (QD), recommended to occur before breakfast, during all parts of the study (see Section 4.3.4), starting at Day -7 of the DEP. If participants are unable to tolerate the PPI, they may attempt to use an H2 blocker per investigator discretion. If neither the PPI nor H2 blocker can be tolerated, the participant will discontinue from the study.

- Decrease the frequency of dosing for 1 to 2 days. This can be initiated without the approval of the medical monitor.
- Skip dosing 1 to 2 days. This can be initiated without the approval of the medical monitor.
- Skip dosing  $\geq 3$  days. This must be discussed with the medical monitor.
- De-escalate to a previous level after discussion with the medical monitor. In this case, the participant will restart 3 weeks at a previously tolerated dose including its ramp, and this previously tolerated dose will be the iTD. After de-escalation, participants cannot escalate to a higher dose again during Part 1.

In general, a dose is considered intolerable if the participant experiences Grade 3 or more severe TEAEs or Grade 2 GI AEs that do not improve with continued dosing at the same dose level over time. If a dose is de-escalated due to a reason other than Grade 3 or greater or Grade 2 GI TEAEs, or a second de-escalation is required, the medical monitor must be consulted. Participants must take at least 8 of the 9 expected doses on the final 3 days of their iTD period. If not, the medical monitor must be consulted before the participant enters Part 2.

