2.2 STUDY DESIGN

This is a 3-part, Phase 3 study consisting of a dose-escalating, open-label period (DEP; Part 1) of up to 15 weeks, followed by a 4-week, double-blind, placebo-controlled, randomized withdrawal period (RWP; Part 2), and an open-label extension (OLE; Part 3) of up to 36 months. [Figure 1](#) presents a study schematic.

In the DEP, all enrolled participants will maintain a stable diet reflecting their baseline Phe intake and receive escalating doses of SYNB1934v1 from approximately 3 to 15 weeks to determine an iTD, which is defined as the highest dose the participant is able to tolerate. A participant will be defined as having reached an iTD if they tolerate 3 weeks at a dose, regardless of whether other doses are tolerated.

Blood Phe level will be measured at each dose level after 3 weeks at that level. A responder will be defined as a participant who achieves a $\geq 20\%$ reduction in blood Phe level compared to DEP baseline on their iTD. For inclusion in the RWP primary efficacy analysis population, response will be assessed at the third week of a participant's established iTD for SYNB1934v1.

If at any time during a 3-week dosing interval in the DEP the participant or investigator considers a dose level to be intolerable, the dose may be de-escalated after discussion with the medical monitor. In this case, the participant will restart 3 weeks at the lower level iTD. After de-escalation, participants cannot escalate to a higher dose again during.

[figure not shown]
The DEP will contain an optional substudy (DEP weekly substudy) to evaluate the range and variability of [REDACTED] at each dose level. The [REDACTED] participants in this substudy will have weekly Phe and Tyr value assessments during the DEP (i.e., with Tyr assessments being primarily assessed for safety).

Once the first [REDACTED] participants have attained an iTD and completed the DEP or the [REDACTED] has a baseline DEP and has been in the study for [REDACTED], whichever occurs earlier, the DEP data will be evaluated by an independent Data Monitoring Committee (DMC). The DMC will use a pre-specified set of criteria based on both safety and efficacy to determine whether the dose regimen is appropriate or whether any doses should be discontinued as well as whether the study should be stopped for futility. Enrollment will not be paused during the interim analysis.

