3.15.1.5 Adverse Event Summaries

The following are the set of adverse event summaries.

- Overall summary of TEAEs
- Incidence of TEAEs by SOC and PT
- Incidence of TEAEs by SOC, PT, and Severity
- Incidence of TEAEs by SOC, PT, and Related to SYNB1934v1

- E.** Incidence of TEAEs by SOC, PT, and Related to PPI
- F.** Incidence of TEAEs Leading to Drug Interruption by SOC and PT
- G.** Incidence of TEAEs Leading to Dose Reduction by SOC and PT
- H.** Incidence of TEAEs Leading to Drug Discontinuation by SOC and PT
- I.** Incidence of AESIs by SOC, PT, and Severity
- J.** Incidence of Serious Adverse Events by SOC and PT
- K.** Incidence of SYNB1934v1 Related Serious Adverse Events by SOC and PT
- L.** Incidence of PPI Related Serious Adverse Events by SOC and PT.

For the DEP only:

- M.** Incidence of Adverse Events prior to first dose of SYNB1934v1 by SOC and PT by Dose Level
- N.** Incidence of Adverse Events prior to first dose of SYNB1934v1 which are PPI related by SOC and PT by Dose Level
- O.** Incidence of TEAEs by SOC and PT by Dose Level
- P.** Incidence of TEAEs by SOC, PT, and Severity by Dose Ramp Period
- Q.** Incidence of TEAEs by SOC, PT, and Related to SYNB1934 by Dose Ramp Period.

This set of analyses will be performed for each of the 3 study periods (DEP, RWP, OLE) separately using the corresponding SAS. The following conventions will be applied:

- For the DEP, the AEs summaries will be presented by SYNB1934v1 dose group and overall. The SYNB1934v1 dose group will be determined by the dose the participant was on at the TEAE start date
- For the RWP, the AEs summaries will be presented by SYNB1934v1 (i.e., each individual iTD dose and overall) and placebo and within these 2 treatment groups by: responder, nonresponder, and overall
- For the OLE, the AE summaries will be presented by responder, nonresponder, and overall. The SYNB1934v1 dose group will be determined by the dose the participant was on at the TEAE start date.

For the presentation of TEAE incidences, the SOCs will be sorted alphabetically, and within SOC, the PT will be used and presented by decreasing total frequency based on the total population.

For the overall summary of TEAEs (i.e., item **A** above), the following information will be provided:

- Number and percent of participants with a TEAE
- Number and percent of participants with a TEAE of Grade 1

- Number and percent of participants with a TEAE of Grade 2

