- Number and percent of participants with a TEAE of Grade 3
- Number and percent of participants with a TEAE of Grade 4
- Number and percent of participants with a SYNB1934v1 related TEAE
- Number and percent of participants with a PPI related TEAE
- Number and percent of participants with an AE leading to treatment interruption
- Number and percent of participants with an AE leading to treatment discontinuation
- Number and percent of participants with an AE leading to dose reduction
- Number and percent of participants with an SAE
- Number and percent of participants with a SYNB1934v1-related SAE
- Number and percent of participants who died.

Additionally, for the adolescent subgroup, TEAEs will be summarized by PT and SOC for each of the 3 study periods (DEP, RWP, and OLE).

- For the DEP, the TEAEs summaries will be presented by SYNB1934v1 dose group and overall. The SYNB1934v1 dose group will be determined by the dose the participant was on at the TEAE start date.
- For the RWP, the TEAEs summaries will be presented by SYNB1934v1 (i.e., each individual iTD dose and overall) and placebo and within these 2 treatment groups.
- For the OLE the TEAEs summaries will be presented by SYNB1934v1 dose group and overall. The SYNB1934v1 dose group will be determined by the dose the participant was on at the TEAE start date.

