3.15.1.7 Adverse Event Summaries Across Study Periods

The analyses specified in [Section 3.15.1.5](#) will be repeated based on the data across all periods (DEP, RWP, and OLE). TEAEs will be summarized across study periods by dose group: placebo, 3×10^{11} , 6×10^{11} , 1×10^{12} and SYNB1934v1 overall. The dose group will be determined by the dose the participant was on at the TEAE start date.

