3.15.1.8 GI Daily Diary Card

As discussed in Section 5.5.1 of the study protocol, participants will fill out a diary card during screening, DEP, and RWP to allow for enhanced capture of the gastrointestinal (GI) AEs. This diary will contain the GI event description start/stop date and the question “*how much did this event bother you?*” with the response being a 0–10-point numeric rating scale with 0 bothered” and 10 bothered”. When the investigator records this event as an AE, the following summaries of the tolerability will be performed:

- For GI TEAEs with a start date in the Screening Period, the tolerability will be summarized by PT and overall.
- For GI TEAEs with a start date in the DEP, the tolerability will be summarized by PT and overall, for each iTD and overall.
- For GI TEAEs with a start date in the RWP, the tolerability will be summarized by PT and overall, for treatment group, and with the active arm, for each iTD and overall.

Note: the other information provided in the GI Daily Diary Card will be incorporated in the adverse event database. For AEs occurring over multiple days, the highest bothersomeness score will be recorded. Should the investigator determine that the event recorded on the daily diary card is not an adverse event, the corresponding GI Daily Diary card entry, including the bothersomeness data, will not be recorded in the adverse event database.

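### RWP adverse events and GI bother scores are split by iTD in the active arm only, so an active dose column read against pooled placebo is not a randomised comparison

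*SAP*

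**What the plan says.** SAP 3.15.1.5 sets out the RWP adverse event tables: "For the RWP, the AEs summaries will be presented by SYNB1934v1 (i.e., each individual iTD dose and overall) and placebo". The only further split made in both arms is by response status: "within these 2 treatment groups by: responder, nonresponder, and overall". The adolescent table in the same section repeats the layout: "For the RWP, the TEAEs summaries will be presented by SYNB1934v1 (i.e., each individual iTD dose and overall) and placebo". For GI bother scores from the diary card, SAP 3.15.1.8 asks for RWP summaries "for treatment group, and with the active arm, for each iTD and overall". The cross-period table in SAP 3.15.1.7 also has a single placebo group: "TEAEs will be summarized across study periods by dose group: placebo", followed by the three dose levels.

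SAP 2.2 describes the iTD as the dose "which is defined as the highest dose the participant is able to tolerate". Protocol 1.6 says what limits it: "Dosing is limited by GI tolerability which appears to be variable across individuals". Under Protocol 3.2 a dose is generally intolerable after a Grade 3 or worse event, or after "Grade 2 GI AEs that do not improve with continued dosing at the same dose level over time".

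The SAP treats the iTD as known for placebo participants too. It is a fixed effect, with a visit interaction, in the RWP primary model (3.14.2.1). It is a variable in the missing-at-random imputation model (3.18.2.1). Its distribution is tabulated by treatment group (3.13.3). No section splits placebo adverse events by iTD.

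**The concern.** Each participant's iTD is established in the DEP, before any RWP treatment, and largely by the kind of event that these tables then count. Participants with the lowest iTD will often be there because they had GI trouble at a higher dose. Active participants at a given iTD and placebo participants at the same iTD are randomised counterparts. Active participants at a given iTD and all placebo participants are not, because the placebo column mixes people with every level of GI tolerance.

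If people with a low iTD also have more GI complaints off drug, the lowest dose column looks worse against pooled placebo than the drug makes it, and the highest dose column looks better. The RWP is the only placebo-controlled part of this trial, so its tables are where a reader of the study report would look for safety by dose against placebo.

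**Working it through.** The plan states no figure that depends on this layout, so there is nothing to reproduce. The check is how far an active iTD column can sit from pooled placebo for reasons other than drug.

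**Formula.** Let p0k be the placebo risk of an event in iTD stratum k, p1k the active risk in that stratum, and wk the share of participants at iTD k. Under 1:1 randomisation the expected share is the same in both arms. Then

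active at iTD k minus pooled placebo = (p1k − p0k) + (p0k − Σ wj·p0j).

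The first bracket is the drug effect in the stratum. The second is the bias. With placebo restricted to iTD k, the second bracket disappears.

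**Inputs.** The documents give neither wk nor p0k. All values below are assumptions, ordered 3×10¹¹ / 6×10¹¹ / 1×10¹². The last two rows take the two upper levels together.

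| Shares (%) | Placebo risks (%) | Pooled placebo (%) | Bias (points) |
|---|---|---|---|
| 30/30/40 | 20/20/20 | 20.0 | 0 / 0 / 0 |
| 30/30/40 | 25/20/15 | 19.5 | +5.5 / +0.5 / −4.5 |
| 30/30/40 | 30/20/10 | 19.0 | +11 / +1 / −9 |
| 30/30/40 | 40/20/10 | 22.0 | +18 / −2 / −12 |
| 50/30/20 | 30/20/10 | 23.0 | +7 / −3 / −13 |
| 15/25/60 | 30/20/10 | 15.5 | +14.5 / +4.5 / −5.5 |
| 25/75 | 40/15 | 21.25 | +18.75 / −6.25 |
| 25/75 | 30/15 | 18.75 | +11.25 / −3.75 |

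Example, third row: 0.30×0.30 + 0.30×0.20 + 0.40×0.10 = 0.19, so the bias at the lowest iTD is 0.30 − 0.19 = +0.11.

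**Effect on a dose trend.** Suppose true drug effects of +5, +10 and +15 points, with shares 30/30/40.

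- Placebo risks 25/20/15: every active column is 30%. Against pooled placebo of 19.5% each dose shows +10.5, so the trend is hidden.
- Placebo risks 30/20/10: the active columns are 35%, 30% and 25%. Against pooled placebo of 19% they show +16, +11 and +6, so the trend is reversed.
- In both cases iTD-matched placebo returns +5, +10 and +15. The overall difference is 0.3×5 + 0.3×10 + 0.4×15 = +10.5 points with either layout.

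**Cell sizes.** The sample size is redacted. The Protocol synopsis gives a difference of 245 µmol/L, SD 247 µmol/L, two-sided alpha 0.05, 5% dropout and about 50% responders. A two-sample t-test then needs 17, 23 or 28 evaluable responders per arm for an assumed power of 80%, 90% or 95%. With dropout that is 36, 49 or 59 responders in total. At 50% responders it is 72, 98 or 118 randomised, or 36, 49 or 59 per arm. At an assumed 25% share, the lowest iTD has about 9 to 15 participants per arm.

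**Precision, with no drug effect and the 40/15 risks.** For 9 per cell, the standard error of a matched difference is √(2×0.40×0.60/9) = 23 points; for 15 per cell it is 18. Against pooled placebo it is √(0.24/9 + 0.2125×0.7875/36) = 18 points, and √(0.24/15 + 0.2125×0.7875/59) = 14. Matching therefore costs about 4 to 5 points of standard error and removes a bias of 18.75 points.

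**The case against.** The strongest reply is that these tables are not a comparison by dose at all. Protocol 8.10 says safety is summarised descriptively by the regimen the participant was on, and a placebo participant's regimen is placebo. No test, risk difference or interval by dose is planned. The overall active column stands beside placebo and keeps the randomised contrast. All of this is correct, and it limits the point to how a dose column is read. It does not make that reading sound: the SAP chose to set dose columns beside placebo, and readers will compare them.

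A reader might infer that dose selection would go the wrong way. The documents do not support that. The dose-dropping criteria (Protocol Table 12, SAP Table 10) use the share of participants attaining each iTD and within-participant Phe reductions in the DEP. No rule uses RWP adverse events.

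A reader might also infer that GI event rates must differ by iTD whatever is taken in the RWP. The documents show dose-related GI events on drug and variable tolerability, but no placebo or off-drug rate by iTD. Nor does a low iTD always mean intolerance: stepping down is also allowed at the investigator's discretion (Protocol Table 5, footnote d), and the ramp changes if doses are dropped (note to Protocol Figure 2). The placebo rate is unlikely to be zero, since all participants continue a PPI or H2 blocker and the SAP itself tabulates GI events before first dose. Whether it varies by iTD is unknown.

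Small cells are a fair objection. The active iTD cells already planned are similarly small, however, and the overall placebo column would remain. Finally, the table shells are a separate document (SAP 3.19) that could not be checked.

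**Conclusion.** The point holds as a flaw in presentation. SAP 3.15.1.5, including its adolescent table, and 3.15.1.8 pair iTD-specific active columns with a placebo group of a different iTD mix. The resulting bias is zero if GI sensitivity appears only on drug. Over the assumed ranges, with placebo risk falling as iTD rises, it runs up to about +18 to +19 points at the lowest iTD and down to about −13 at the highest. These figures are illustrations; only the formula and the direction under that assumption are firm.

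The randomisation of the trial, the overall active-versus-placebo safety contrast, the efficacy analyses and the interim rules are all untouched. Matching on iTD restores a randomised comparison within each iTD. It does not make comparisons between doses randomised, because each dose is still taken by different people. For bother scores, which are summarised only for recorded GI events, matching removes the difference in iTD mix but the summary remains conditional on having an event.

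**What to change.** In SAP 3.15.1.5 and 3.15.1.8, present RWP placebo participants by their own iTD as well as overall, so that each active iTD column has its randomised counterpart beside it. Specify this before the lock and unblinding that follow the RWP (SAP 2.2.3).

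Within responder status and in adolescents the cells may be nearly empty; there the iTD split can be limited to the overall table, provided it is then dropped for both arms.

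In SAP 3.15.1.7, add a footnote that the pooled placebo group is not iTD-matched to the dose columns. Those columns follow the dose at event onset across all periods, so a footnote is enough.

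The cost is SAP wording and table shells. No new data are needed, because the iTD is already held for every randomised participant. The downside is wide uncertainty in the small placebo cells, so counts and denominators should be shown with the percentages.

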3.15.1.6 Adverse Events by Dose Ramp Day

For the DEP, adverse events will be analyzed relative to the Dose Ramp Schedule (see Table 8).

Specifically, TEAEs will be summarized by dose level (3×10^{11} , 6×10^{11} , 1×10^{12}) and within dose level by the dose frequency schedule.

The Dose Ramp Days will be partitioned as follows for each of the 3 doses (i.e., as described in Table 4 of the study protocol):

- 3×10^{11} : Days 1-3, 4-6, 7-9, 10-11, 12-14, and 15-21 (as well as “Overall”)
- 6×10^{11} : Days 1-3, 4-7, and 8-21 (as well as “Overall”)
- 1×10^{12} : Days 1-3, 4-7, and 8-21 (as well as “Overall”).

The SYNB1934v1 dose level and Day period will be determined by the dose and dose ramp day the participant was on at the TEAE start date. The denominator will include all participants who received at least one dose within the corresponding dose ramp day period (i.e., this calculation will be based on a participant's first and last dose day within a dose level). This will also include TEAEs which occur while a participant is on a particular dose level (e.g., if a participant is on 3×10^{11} at two different times during the DEP, both of these periods will be included when assessing participants TEAEs at the 3×10^{11} dose).

These summaries will be:

- Incidence of TEAEs by PT and SOC
- Incidence of TEAEs Leading to Dose Reduction by SOC and PT
- Incidence of TEAEs Leading to Drug Discontinuation by SOC and PT.

Additionally, within each dose ramp, a “per-day” rate of adverse events will be calculated with the numerator being the number of participants with the corresponding TEAE and the denominator being the sum of the number of days the participants were in the dose ramp period. The summaries will be:

- Per-Day rate of TEAEs by PT and SOC
- Per-Day rate of TEAEs Leading to Dose Reduction by SOC and PT
- Per-Day rate of TEAEs Leading to Drug Discontinuation by SOC and PT.

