- ***MMRM Analysis by Dose Level:*** The percent change in blood Phe level will be analyzed using an MMRM model. All available Week 3 blood Phe data will be used. The model will have percent change from baseline as the dependent variable. Dose level (as a categorical variable) and baseline blood Phe will be fixed effects. The MMRM analysis will be based on the restricted maximum likelihood method. A Kenward-Roger approximation will be used for the denominator degrees of freedom. The covariance structure for the repeated-measures will be a direct product of unstructured for the multiple Week 3 visits (i.e., a total of 5 possible Week 3 visits, 3 for each dose level and 2 for possible repeats of the 3×10^{11} and 6×10^{11} doses) and compound symmetry for the repeated assessments at a particular visit. As such the covariance structure will use the direct product structure “UN@CS” as defined in SAS PROC Mixed.

This will be an observed-case analysis, this analysis will be performed using the DEP FAS and also using the responder RWP FAS population, missing data will not be imputed.

If the MMRM analysis does not converge, the repeated measures at each blood Phe assessment will be averaged together and the average of the repeated measures will be used to calculate the percent change in blood Phe level, the dependent variable. The model will have percent change from baseline as the dependent variable (i.e., using the averaged value at Week 3 visit). The MMRM model will be the same (i.e., same set of fixed effects) with the exception that the covariance structure for the repeated-measures will be unstructured for the multiple Week 3 visits (i.e., a total of

5 possible Week 3 visits, 3 for each dose level). If this model does not converge a compound symmetry covariance structure will be used.

Additionally, histograms illustrating the DEP Week 3 change and percent change from baseline in blood Phe by treatment group will be produced, overall and by iTD.

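### The DEP dose-ramp AE tables pool first and repeat passes at a dose, which can only shrink the incidence gap to the top dose or leave it unchanged, and usually moves the per-day rates the other way

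*SAP*

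**What the plan says.** SAP 3.15.1.6 tabulates DEP TEAEs by dose level and, within dose, by ramp-day bin. An event is assigned to the dose and ramp day at its start date. The section then pools passes: for a participant on 3×10^11 "at two different times during the DEP, both of these periods will be included when assessing participants TEAEs at the" 3×10^11 dose.

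Two kinds of table follow.

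- Incidence: "The denominator will include all participants who received at least one dose within the corresponding dose ramp day period".
- Per-day rate: "the numerator being the number of participants with the corresponding TEAE and the denominator being the sum of the number of days" spent in the ramp period.

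The by-dose DEP tables in SAP 3.15.1.5 also use the dose at event onset, so they merge the passes too. No AE table confined to the first pass, or to the repeat pass, is planned.

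Protocol 3.2 explains how a repeat arises. After de-escalation, "the participant will restart 3 weeks at a previously tolerated dose including its ramp, and this previously tolerated dose will be the iTD". The same section and the synopsis rule out a later escalation in Part 1. SAP 3.14.1.3 counts the windows this creates: "a total of 5 possible Week 3 visits, 3 for each dose level and 2 for possible repeats of the" 3×10^11 and 6×10^11 doses.

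**The concern.** These tables should show at which dose and ramp step AEs arise. Protocol 1.6 names GI tolerability as the limit on dosing, and Protocol 1.5.1 reports that GI events rose with dose in an earlier study.

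Pooling treats the doses unequally. The two lower doses can each hold two 3-week windows for the same person; the top dose can hold only one. The second window is also not a random sample, since it comes mainly from participants who had trouble with the next dose. A reader comparing columns would be comparing different lengths of observation and a different mix of people without being told so.

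**Working it through.** **Step 1. Number of windows.** Three first passes plus two repeats give 5 windows, and 5 × 21 days = 105 days. This equals the maximum iTD-finding period in Protocol Table 5, so repeats are built into the design.

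**Step 2. Direction in the incidence tables.** At a lower dose let n be the participants, a those with the TEAE on the first pass, and b those whose only such TEAE is on the repeat.

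- First pass: a/n. Pooled: (a + b)/n.
- A repeater has already completed that dose, so n does not change, and b ≥ 0.
- The 1×10^12 column has no repeat and does not move.

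The gap from either lower dose to the top dose can therefore only shrink or stay the same, whatever the rates.

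**Step 3. Direction in the per-day tables.** Let D be first-pass days and d repeat days.

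- First pass: a/D. Pooled: (a + b)/(D + d).
- The pooled rate is lower whenever b/d < a/D.
- As the numerator is worded, a repeater with an earlier event adds days to d and nothing to b, which makes this the usual result.

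This reading takes repeat days as included in the sum. The SAP implies that but does not say it.

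**Step 4. Size.** The documents give no AE or de-escalation rates, so every rate here is an assumption. I simulated 400,000 participants per scenario, varying:

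- 21-day AE probability at the lowest dose: 30% or 50% (before frailty);
- hazard ratio per dose step: 1.3, 1.6 or 2.0;
- log-normal frailty SD: 0 or 1;
- probability that an AE leads to de-escalation: 0.3 or 0.6;
- repeat-pass hazard: ×0.5 (adaptation) or ×1.0.

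That gives 2 × 3 × 2 × 2 × 2 = 48 scenarios. Three of them, as low/mid/top dose:

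| Scenario (AE probability, HR, frailty SD, de-escalation, repeat hazard) | Incidence %, first pass | Incidence %, pooled | Per 1000 days, first pass | Per 1000 days, pooled |
|---|---|---|---|---|
| A: 30%, 1.6, 1, 0.3, ×1.0 | 25.2/33.6/42.9 | 27.5/36.1/42.9 | 12.5/16.8/21.9 | 12.3/16.3/21.9 |
| B: 50%, 2.0, 0, 0.6, ×0.5 | 50.2/75.1/93.6 | 58.1/82.1/93.6 | 28.0/47.4/69.4 | 23.0/38.4/69.4 |
| C: 50%, 1.3, 1, 0.6, ×1.0 | 39.5/41.0/43.0 | 45.9/46.5/43.0 | 21.4/22.4/23.6 | 20.4/21.3/23.6 |

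Top-minus-low gaps (per-day gaps taken from unrounded rates):

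- A: incidence 42.9 − 25.2 = 17.7 points falls to 42.9 − 27.5 = 15.4. The per-day gap goes from 9.5 to 9.6.
- B: incidence 93.6 − 50.2 = 43.4 falls to 93.6 − 58.1 = 35.5. The per-day gap goes from 41.3 to 46.4.
- C: incidence 43.0 − 39.5 = +3.5 becomes 43.0 − 45.9 = −2.9. The per-day gap goes from 2.2 to 3.2.

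Across the 48 scenarios:

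- Pooling raised incidence by about 1.0 to 14.7 points at 3×10^11 and 1.2 to 11.4 points at 6×10^11.
- A first-pass gradient that rose with dose was reversed in 4, all with HR 1.3 per step and de-escalation probability 0.6.
- The per-day top-minus-low gap widened in 46, tied in 1, and narrowed by 0.1 per 1000 days in 1.

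**The case against.** The strongest reply is that assigning safety data to the regimen at the time is a stated convention (Protocol 8.10), and that the section already plans per-day rates to deal with unequal time. Other outputs also bear on tolerability by dose: TEAEs leading to dose reduction or discontinuation by ramp day, and time on a level the participant discontinued from (SAP 3.13.2). The tables are descriptive, and the numeric criteria in SAP Table 10 use iTD attainment, DEP completion, Phe reduction and response.

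Much of that stands, and it limits the weight of the point. The per-day tables do not cure the problem, though: they bend the comparison in the other direction and still do not isolate the escalation ramp.

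A reader might infer more than the documents support:

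- *That lower-dose exposure absorbs days spent on the higher dose.* The phrase "first and last dose day within a dose level" sits in the sentence on who enters the incidence denominator. Days for the rates are defined separately, as days in the ramp period.
- *That repeat-pass events fall outside the Day 1–21 bins.* A repeat restarts with its ramp, so it has its own ramp days within the grid.
- *That the SAP separates repeats for Phe but not for safety.* The five visits in SAP 3.14.1.3 define the covariance structure. The fixed effect is dose level, so passes share one dose effect there too.
- *That every repeater failed the next dose.* Footnote d to Protocol Table 5 also allows stepping down at the investigator's discretion.

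**Conclusion.** The point holds as a presentational distortion in descriptive safety tables. The direction for incidence follows from the design alone: the gap from either lower dose to 1×10^12 is reduced or unchanged. The direction for per-day rates is usual rather than certain, and rests on repeat days being summed while each participant counts once. One pooling rule therefore pushes two sets of tables in the same section in opposite directions.

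The size cannot be fixed from the documents. In the assumed scenarios it runs from about 1 point of incidence to more than 10. Reversal of the dose gradient is not a general result: it appeared in 4 of 48 scenarios, needed a shallow gradient with frequent de-escalation, and no documented rate supports it. Protocol 1.6 says titration improved tolerability, which would make repeat-pass events fewer.

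No efficacy test and no numeric dose-dropping criterion is affected. Because SAP Appendix 3 applies the SAP's methods to DMC outputs, pooled tables could still be what the DMC reads on safety.

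**What to change.** In SAP 3.15.1.6, and in the by-dose DEP tables of 3.15.1.5:

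- Keep the pooled tables if wanted, labelled as pooled.
- Add first-pass (escalation) incidence and per-day rates by dose and, where that table uses them, ramp-day bin.
- Show the repeat pass in separate columns for 3×10^11 and 6×10^11, with its own denominator and the ramp day restarted.
- For per-day rates, count participants and days within each pass, and say so.

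The cost is SAP wording and a few descriptive columns. The start and stop dates by dose level that SAP 3.13.1 already uses for compliance are enough, so no new data are needed. Repeat-pass numbers will be small. The change does not remove a second selection: only participants who tolerated the lower doses reach 1×10^12, and this can flatten a first-pass gradient as well. A footnote should say that.
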